Additional exclusion criteria to be applied after data extraction to create an *unexposed source population* (mirroring the exposed source population, except for the exposure itself):

- Women treated with anifrolumab during pregnancy and/or during the 16-week period prior to LMP2
- Pregnancies whose date of conception cannot be established

STEP 3

Step to create *exposed to anifrolumab study population* and *unexposed to anifrolumab study population*.

STEP 3A and 3B – exposed and unexposed to anifrolumab study population

Additional inclusion criteria to be applied to the exposed and unexposed source population for creating a post-data extraction overarching *exposed and unexposed study population* with only moderate to severe SLE (mirroring the exposed study population, except for the exposure itself):

- Women with moderate to severe SLE (severity assessment is based on the SLE severity algorithm, see Figure 7)

Additional exclusion criteria to be applied to the exposed and unexposed source population for creating a post-data extraction overarching *exposed and unexposed study population* (mirroring the exposed study population, except for the exposure itself):

- Women with mild SLE (severity assessment is based on the SLE severity algorithm, see Figure 7)

⁷ For example, a patient can be considered continuously enrolled in a specific time period if that patient had a contact with healthcare services (such as drug prescription/administration or hospitalisation) prior to that period and if emigration or death were not notified after this contact. Criteria to define continuous enrolment in the database are country specific and will be detailed in the SAP.

⁸ Exposure to SLE SOC will be assessed from LMP2 until end of first trimester for the outcome of MCM, and from LMP2 until end of pregnancy for all other outcomes. A look-back period of 5-half-lives of relevant drugs will be considered.

- Women with a history of CM or chromosomal abnormalities and genetic syndromes (according to available records)⁹, before delivery
- Women prescribed a confirmed teratogenic drug prior to LMP2 until end of first trimester (for MCM outcome) or end of pregnancy (all other pregnancy outcomes), with a look back period of 5-half-lives of relevant drug, in both the exposed and unexposed groups (see [Table 20](#))

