To address the research questions related to the primary, secondary, and exploratory outcomes, cohorts and subgroups will be created. Additional selection criteria, to form the relevant population for each specific outcome, will be applied (*STEP 4*).

STEP 4 - Cohorts and sub-cohorts

For the purpose of the evaluation of MCM (primary outcome), the *MCM* cohort will be derived from the study populations ([Table 5](#)) and will include live and non-live offspring from mothers diagnosed with SLE (regardless of the exposure to anifrolumab, i.e., sub-cohorts *MCM_exp+MCM_unexp*).

For the purpose of the evaluation of mCM (secondary outcome), the *mCM* cohort will be derived from the study populations ([Table 5](#)) and will include live and non-live offspring from mothers diagnosed with SLE (regardless of the exposure to anifrolumab, i.e., sub-cohorts *mCM_exp+mCM_unexp*).

For the purpose of the evaluation of select pregnancy loss outcomes (composite of spontaneous abortion and stillbirth; primary outcome), and secondary outcomes (adverse pregnancy outcomes), the *pregnancy* cohort will be derived from the study populations ([Table 5](#)) and will include pregnant women diagnosed with SLE (regardless of the exposure to anifrolumab, i.e., sub-cohorts *pregnancy_exp+pregnancy_unexp*).

For the purpose of the evaluation of adverse birth outcomes (secondary outcomes), the *birth* cohort will be derived from the study populations ([Table 5](#)) and will include live offspring from mothers diagnosed with SLE (regardless of the exposure to anifrolumab, i.e., sub-cohorts *birth_exp+birth_unexp*).

For the purpose of the evaluation of adverse outcomes related to infant growth up to one year of age, the *infant* cohort will be derived from the study populations ([Table 5](#)) and will include live offspring from mothers diagnosed with SLE (regardless of the exposure to anifrolumab, i.e., sub-cohorts *infant_exp+infant_unexp*).

⁹ Several CMs in the mother are due to genetic syndromes/ microdeletions and chromosomal abnormalities which are heritable. These genetic syndromes/microdeletions are also causally associated with the outcomes of interest. The list of these syndromes/microdeletions and chromosomal abnormalities are provided in [Appendix D. Exemplar Codelists](#).

Additional inclusion and exclusion criteria to derive the abovementioned cohorts and sub-cohorts are listed in [Table 5](#).

Table 5: Cohorts and sub-cohorts as described in STEP 4, by objective

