MCM (defined as a composite of all major MCMs) among live and non-live offspring: The first primary outcome of interest is MCM occurring in live or non-live offspring. MCM is defined as defects of prenatal origin that have either cosmetic or functional significance to the child's health, development, or survival. MCM ascertainment will be based on the presence of an ICD-10 code (or other database specific coding system [codes to be adapted to the coding systems used in each of the data sources]) in the database. These ICD-10 codes will be classified according to the EUROCAT (Description of the Congenital Anomaly Subgroups in EUROCAT Guide 1.5) classification scheme, as four of the five data sources are in Europe (41). As there are some differences in the classification of MCMs by different classification schemes, the USA CDC definition of MCM as an abnormality of body structure or function that is present at birth, is of prenatal origin (i.e., birth defect), has significant medical, social, or cosmetic consequences for the affected individual, and typically requires medical intervention as implemented by the Metropolitan Atlanta Congenital Defects Program (MACDP) will also be implemented as a sensitivity analysis (see Section 9.7.5) (15, 24). The list of the MCM and their respective ICD-10 codes are presented in Table 22a using the EUROCAT classification. The MACDP 6-digit code defect list for major congenital malformations is presented in Table 22b.

The MCM ascertainment period is defined as:

- for live births, from birth until 1 year of age
- for non-live births (spontaneous abortion and stillbirth) an ICD-10 of MCM as the diagnosis at end of pregnancy
- for elective terminations, an ICD-10 code of an MCM as the reason for the termination at termination of pregnancy.

Select pregnancy loss outcomes (composite of spontaneous abortion and stillbirth) among all pregnancies

The second primary outcome of interest is select pregnancy loss outcomes, a composite of spontaneous abortion and stillbirth (Table 24).

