- **Proportion of unexposed to confirmed teratogenic SLE SOC and/or non-SLE SOC drugs of 80%.** It is estimated that 80% of the SLE pregnancies are not exposed to SLE SOC and non-SLE SOC confirmed teratogenic drugs before conception, with a time period of 5-half-lives of relevant drug (see list of confirmed teratogenic drugs and half-lives in Table 20), or during pregnancy. This estimate is based on the reported use of SLE SOC and/or non-SLE SOC drugs in SLE population (47, 48).
- **Proportion of anifrolumab exposure during the first trimester of pregnancy of 80%.** The majority of the anifrolumab exposed pregnancies are expected to be unplanned and exposed to anifrolumab only in the early stages of the pregnancy, as the current recommendations indicate that anifrolumab should only be used during pregnancy if the benefit outweighs the risk to the foetus (86). We therefore used the assumption that 80% of all anifrolumab exposed pregnancies are exposed to anifrolumab during the first trimester of pregnancy.
- **Proportion of anifrolumab exposed pregnancies in women with moderate-to-severe SLE of 5% and 10%.** Based on market forecasts, uptake of anifrolumab in the general SLE population is expected to grow from 5% within two years of market launch to 20% by 5 years after market launch. Given the uncertainty of how these forecasts apply to SLE women of child-bearing potential and to use in pregnant SLE women, we used a conservative lower bound (5%) and a more realistic midpoint value (10%) for the proportion of pregnancies in women with moderate-to-severe SLE exposed to anifrolumab.

In addition, to estimate the minimum required sample size and the expected power, the following assumptions were used:

- **Non-inferiority margin of RR of 2.5.** The RR of 2.5 was based on previously reported increase in risk of MCM for exposure to a major teratogenic drug (62).

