Appendix D. Exemplar Codelists

Codelists included in this appendix are still under development and will be finalised in the SAP.

Table 18: Inclusion and exclusion criteria for the overall study population, EXEMPLARY codelist

Inclusion criteria for the overall source population	ICD-10
Systemic lupus erythematosus	
Systemic lupus erythematosus with organ or system involvement	M32.1
Other forms of systemic lupus erythematosus	M32.8
Systemic lupus erythematosus, unspecified	M32.9
Exclusion criteria for the overall source population	ICD-10
Multifetal pregnancies	
Multiple gestation	O30
IVF	
In vitro fertilisation	Z31.2

Abbreviations used in the table: ICD-10, International statistical classification of diseases tenth revision; IVF, In vitro fertilisation

Table 19: Drug classes and active substances used in SLE SOC ¹

Drug/Procedure	ATC codes
Antimalarials	
Chloroquine	P01BA01
Hydroxychloroquine	P01BA02
Quinacrine (mepacrine)	P01AX05
Glucocorticoids	
Dexamethasone	H02AB02
Methylprednisolone	H02AB04
Prednisolone	H02AB06
Prednisone	H02AB07
Triamcinolone	H02AB08
Immunosuppressive agents	
Biologic immunosuppressants	
Anifrolumab (drug of interest)	L04AA51
Belimumab	L04AA26
Rituximab (including reference product and biosimilars)	L01FA01
Synthetic immunosuppressants	
Anakinra	L04AC03
Apremilast	L04AA32
Azathioprine	L04AX01
Baricitinib	L04AA37
Cyclophosphamide	L01AA01
Cyclosporine	L04AD01
Leflunomide	L04AA13

Drug/Procedure	ATC codes
Methotrexate	L04AX03
Mycophenolic acid/sodium ¹	L04AA06
Sirolimus	L04AA10
Tacrolimus	L04AD02
Thalidomide	L04AX02
Tofacitinib	L04AA29
Voclosporin	L04AD03
Immunoglobulins	
Immunoglobulin G	J06BA02
Plasmapheresis	
Plasmapheresis (procedure)	B05AX03

Abbreviations used in the table: ATC, Anatomical therapeutic chemical classification system

¹ drugs that have been investigated in failed SLE clinical trials have not been included in the list of SLE SOC drugs. The list does not consider emerging therapeutic agents (in phase II/III development), of which the efficacy in the management of SLE has not been established.

² As Mycophenolate Mofetil.

Table 20: Confirmed teratogenic drugs

This list has been developed and will be continually updated based on the data available in the TERIS database of teratogenic agents and recent publications ([44](#), [88](#), [109](#), [122](#))

Drug Class	Generic Name	ATC code	Half Life	Pre-Conception Exposure Window ¹	Relevant Exposure Window

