Subgroups	ICD 10-major	ICD-10 -minor (EXCLUDE)
	Q74	Q665 Q666 Q667 Q668 Q669 Q670 Q671 Q672 Q673 Q674 Q675 Q676 Q677 Q678 Q680 Q6810 Q6821 Q683 Q684 Q685 Q7400 Q661
Other anomalies/syndromes	Q0435 Q044 Q206 Q240 Q3381 Q411 Q412 Q418 Q710 Q712 Q7180 Q720 Q722 Q7280 Q730 Q750 Q793 Q7980 Q7982 Q86	No code

Subgroups	ICD 10-major	ICD-10 -minor (EXCLUDE)
	Q8680 Q8706 Q8708 Q8724 Q8726 Q890 Q893 Q894 Q8980 P350 P351 P354 P358 P371	
Genetic disorders	D821 Q4471 Q6190 Q7402 Q7484 Q751 Q754 Q7581 Q77 Q780 Q781 Q782 Q783 Q784 Q785 Q786 Q788 Q789 Q796 Q800 Q801 Q802 Q803 Q804 Q808 Q809 Q810 Q811	No code

Subgroups	ICD 10-major	ICD-10 -minor (EXCLUDE)
	Q812	
	Q818	
	Q819	
	Q820	
	Q821	
	Q822	
	Q823	
	Q824	
	Q8282	
	Q8283	
	Q850	
	Q851	
	Q8581	
	Q87	
	Q8934	
	Q90	
	Q91	
	Q92	
	Q93	
	Q96	
	Q97	
	Q98	
	Q99	

Abbreviations used in the table: ICD-10, International statistical classification of diseases tenth revision; GA, Gestational age

Table 22b: MACDP 6-Digit Code Defect List [XLS – 114 KB] ([CDC BPA Code](#))

Table 23: Minor Congenital Malformations, EXEMPLARY codelist

Subgroups	ICD-10
Nervous System anomalies	Q0780 Q0782 Q0461
Eye anomalies	Q101 Q102 Q103 Q105 Q135 Q752 H046 H052
Ear, face and neck anomalies	Q170 Q171 Q172 Q173 Q174 Q175 Q179 Q180 Q181 Q182 Q184 Q185 Q186 Q187 Q1880 Q189 Q6741
Congenital Heart Defects	Q2111 Q246 Q250 if GA <37 weeks Q2541 Q256 if GA <37 weeks Q261 Q270 R011 I517 I429
Respiratory anomalies	Q314 Q3140 Q315 Q320 Q322

Subgroups	ICD-10
	Q3300 Q3310 Q331
Oro-facial clefts	Q357
Gastro-intestinal anomalies	Q381 Q382 Q3850 Q400 Q401 Q4021 Q430 Q4320 Q4381 Q4382 Q444 Q4583 Q8911 K409 R160 R161
Congenital anomalies of kidney and urinary tract (CAKUT)	Q610 Q627 Q633
Genital anomalies	Q523 Q525 Q527 Q5520 Q5521 Q501 Q5010 Q5011 Q502 Q505 Q53 Q530 Q544 E250 N44 N47 P835
Limb anomalies	Q653 Q654 Q655 Q656

Subgroups	ICD-10
	Q658 Q659 Q662 Q663 Q664 Q665 Q666 Q667 Q668 Q6680 Q669 Q670 Q671 Q672 Q673 Q674 Q675 Q676 Q677 Q678 Q680 Q6810 Q6821 Q683 Q684 Q685 Q7400 Q661 Q8280 Q845 Q846
Other anomalies/syndromes	Q6740 Q753 Q833 Q8281 Q8252 Q8250 Q825 Q8251 Q7660 Q7662 Q765 Q7643 Q760

Subgroups	ICD-10
	Q7671 Q899
Genetic disorders	Q95 Q952

Abbreviations used in the table: ICD-10, International statistical classification of diseases tenth revision; GA, Gestational age

Table 24: Adverse pregnancy outcomes, EXEMPLARY codelist

Adverse outcomes	Description	ICD-10
Ectopic pregnancy	Ectopic pregnancy	O00
Spontaneous abortion	Spontaneous abortion	O03

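### The primary MCM composite counts chromosomal and single-gene disorders in the offspring and no planned RR leaves them out, which pulls the RR towards 1 in a study meant to rule out 2.5

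*Protocol*

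**What the plan says.** Section 9.3.2 sets the outcome as "MCM (defined as a composite of all major MCMs) among live and non-live offspring" and adds: "The list of the MCM and their respective ICD-10 codes are presented in Table 22a using the EUROCAT classification". In Appendix D, Table 22a has a row "Genetic disorders" in its column of major codes. The row begins "D821 Q4471 Q6190 Q7402 Q7484 Q751" and runs through Q77-Q78, Q80-Q82, Q85 and Q87 to the chromosomal blocks Q90-Q93 and Q96-Q99. The column for minor codes to be excluded is empty for this row. The appendix opens with a caveat: "Codelists included in this appendix are still under development and will be finalised in the SAP".

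The genetic exclusion in section 9.2.2, Step 3, concerns the mother: "Women with a history of CM or chromosomal abnormalities and genetic syndromes (according to available records". Its footnote gives the reason: "Several CMs in the mother are due to genetic syndromes/ microdeletions and chromosomal abnormalities which are heritable". The notes under Table 7 list adoption as the only offspring-level exclusion. Objective 15 (section 9.7.4) describes MCM risk by organ class without an RR. The MACDP analysis in section 9.7.5 changes the classification scheme and does not say that genetic cases are dropped.

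On the margin, section 9.5.1.1 states: "The RR of 2.5 was based on previously reported increase in risk of MCM for exposure to a major teratogenic drug".

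**The concern.** The Abstract limits MCM exposure to the first trimester because that is when malformations are expected to arise. Aneuploidies and inherited single-gene disorders are, for the most part, already determined by then. If they occur at the same rate in both groups, they add equal risk to numerator and denominator and shrink the ratio. In a study looking for a difference, that would cost power. In a study that declares success when the upper confidence bound falls below 2.5, it makes success easier to reach when the drug does harm. Section 9.9 makes the same kind of point about non-differential outcome misclassification, but does not mention these cases.

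**Working it through.** **Inputs from the protocol.** MCM risk 7% (9.5.1.1). True RR 1.0, one-sided 2.5%, log-link Poisson within source and inverse-variance fixed effect across sources (9.5.1.3). Required exposed 210 at 1:2 or 183 at 1:3 (9.5.2). Expected exposed in the three contributing sources at 10% uptake in 2032: 102 + 114 + 116 = 332 (Table 11). At 5% uptake: 51 + 56 + 58 = 165 (Table 10).

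**Input not in the protocol.** f, the genetic share of MCM cases in the comparator group. Assumed range 5% to 25%.

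**Step 1: reproduce the plan.** Simulating the procedure of 9.5.1.3 gives:

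| Exposed, ratio | Simulated power | Stated |
|---|---|---|
| 210, 1:2 | 80% | 80% |
| 183, 1:3 | 79% | 80% |
| 332, 1:2 | 96% | 96% |
| 332, 1:3 | 98% | 98% |
| 165, 1:2 | 66% | 69% |

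The sample-size arithmetic holds at 10% uptake. At 5% uptake it comes out about three points below the stated figure.

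**Step 2: attenuation.** If genetic cases have RR 1 and the rest have RR_ng:

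composite RR = f + (1 − f) × RR_ng.

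With RR_ng = 2.5 and f = 10%: 0.10 + 0.90 × 2.5 = 2.35. Conversely, a composite upper bound of 2.5 excludes only RR_ng = (2.5 − f)/(1 − f). At f = 10% that is 2.40/0.90 = 2.67.

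**Step 3: false rule-out.** The same simulation with comparator risk 7%, exposed risk 7% × composite RR, 332 exposed at 1:2, and a true non-genetic RR of 2.5:

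| f | Composite RR | Non-genetic RR excluded | Chance of ruling out 2.5 |
|---|---|---|---|
| 0% | 2.50 | 2.50 | 1.7% |
| 5% | 2.43 | 2.58 | 2.5% |
| 10% | 2.35 | 2.67 | 3.7% |
| 15% | 2.28 | 2.76 | 5.4% |
| 25% | 2.13 | 3.00 | 10% |

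The f = 0 row lies below 2.5% because the Poisson standard error used in the plan's simulation is larger than the binomial one.

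**Step 4: power without genetic cases.** Comparator risk becomes 7% × (1 − f), with true RR 1 and 1:2:

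| f | 332 exposed (10% uptake, 2032) | 165 exposed (5% uptake, 2032) |
|---|---|---|
| 0% | 96% | 66% |
| 10% | 94% | 59% |
| 25% | 88% | 46% |

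The exposed number needed for 80% power at 1:2 rises from 210 to about 234 at f = 10% and 248 at f = 15%.

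**The case against.** The strongest reply is that Table 22a is labelled exemplary and the lists are to be settled in the SAP. That stands as a caveat. But section 9.3.2 fixes the outcome as every major malformation, the table deliberately places genetic disorders among them, and nothing signals that they will be removed.

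The second reply is that the size is assumed. That also stands: at f = 5% the false rule-out rate is no higher than the planned 2.5%, and it takes a share well above 10% to do clear damage.

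Four stronger readings are tempting but unsupported:

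- A reader might infer that the protocol contradicts itself by excluding mothers with genetic syndromes while counting such cases in offspring. The footnote's ground is that maternal conditions are heritable and associated with the outcomes, which is control of maternal risk. Nowhere does the protocol call offspring cases drug-attributable.
- A reader might infer that the drug cannot cause anything in the row. The protocol does not say so, Q87 is a mixed block, and counted exposure includes the 16 weeks before LMP2. The defensible statement is that these cases are largely determined at or before conception.
- A reader might infer that the 2.5 margin came from a study limited to non-genetic malformations. The definition used in that source cannot be seen here.
- A reader might infer that the remedy is to delete every offspring with a code from the row. The rows overlap. The genetic row lists all of Q87, while Q8703 is listed under nervous system anomalies and Q8706, Q8708, Q8724 and Q8726 under other anomalies/syndromes. Deleting the whole row would discard malformations that the table also classes elsewhere, and so lose safety signal.

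**Conclusion.** The point holds as one of outcome definition and direction of bias. Followed as written, the plan's only MCM RRs include offspring cases not expected to respond to exposure, and the resulting attenuation favours a conclusion of safety. Over the assumed 5% to 25% share, a non-genetic RR of 2.5 reads 2.43 to 2.13, and the chance of wrongly ruling it out runs from about 2.5% to about 10%. This rests on the assumed f, on RR 1 for the genetic cases, and on the plan's own 7% risk and 332 exposed. It is worth correcting before the SAP is final. It does not show that the sample-size calculation is wrong.

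**What to change.** Add a prespecified non-genetic MCM composite with its own adjusted RR in each data source and its own pooled estimate. Report it beside the all-MCM result, or make it primary and keep all-MCM as a sensitivity analysis. Require that any conclusion ruling out 2.5 for MCM also hold on it.

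Define the excluded set as clearly chromosomal and monogenic codes, such as Q90-Q93, Q96-Q99 and the single-gene entries of the row. First resolve the overlaps in Table 22a: Q8703, Q8706, Q8708, Q8724 and Q8726 remain cases. Entries such as Q4471, Q6190 and Q7402, which fall inside the organ blocks Q44, Q61 and Q74, need an explicit assignment. State how an offspring with both a chromosomal and a structural code is counted. The split needs clinical review.

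The cost is fewer events. Because the conclusion must hold on the non-genetic composite, power for that conclusion cannot exceed the Step 4 figures: at 1:2 in 2032, about 94% (f = 10%) or 88% (f = 25%) at 10% uptake, and about 59% or 46% at 5% uptake. If the non-genetic composite becomes primary, the 7% prevalence, the required sample size and Table 13 must be restated. Section 9.4 already allows for a longer study period or more data sources if numbers fall short.
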